1.2 Study objectives and endpoints

2 Statistical methods

This section contains information that will be used to draft CSR Section 9.7 on statistical analysis.

2.1 Data analysis general information

All statistical analysis will be performed by Novartis Business Services CONEXTS (NBS CONEXTS). Data will be analyzed by statistical software SAS version 9.4 according to the data analysis section 9.6 of the study protocol.

2.1.1 General definitions

Summary statistics for continuous variables will include N (the number of subjects in the analysis set), n (the number of subjects with available/imputed value), mean, standard deviation (SD), median, minimum & maximum. Summary statistics for discrete variables will be presented in contingency tables and will include absolute and relative frequencies for non-missing data. A row (category) denoted “Missing” will be included in count tabulations if a non-zero count of missing values is present. Percentages will be calculated using the number of patients in the relevant population or subgroup as the denominator. If a count of zero is obtained, the zero count and percentage will still be displayed.

Unless otherwise stated, the level of significance will be set to 5% (two-sided).

2.1.1.1 Study Treatment and Study Day

The day when the patients complete core phase (Week 28) and enter extension period is defined as study Day 1 for Extension phase.

$$\text{Study day} = [\text{Date of event}] - [\text{Date of first extension phase assessment}] + 1$$

2.2 Analysis sets

The following analysis sets will be used for the data analysis.

Safety Set (SAF): The SAF will consist of all patients who received at least 1 dose of study treatment.

Full Analysis Set (FAS): The FAS will consist of all patients who completed the Core phase of the study and either discontinued or entered the extension period.

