5.6 Study completion and discontinuation

5.6.1 Study completion and post-study treatment

A patient will be considered to have completed the core study when the patient has completed the last visit planned of the core study. During the following extension period lifestyle intervention is offered to all patients. Patients from arm B can continue their already ongoing lifestyle intervention, patients from arm A can start a lifestyle intervention. In case a patient from arm B does not want to continue his lifestyle intervention during the extension period or a patient from arm A does not want to start a lifestyle intervention, he still has to participate in the extension period, which means he has to show up for dermatological study visits during the extension period.

During the extension phase no study drug will be supplied by Novartis. Investigators or treating physicians are free to choose suitable therapies for continued psoriasis treatment.

The investigator must provide follow-up medical care for all subjects who are prematurely withdrawn from the study, or must refer them for appropriate ongoing care.

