5.6.5 Early study termination by the sponsor

The study can be terminated by Novartis at any time for any reason. This may include reasons related to the benefit risk assessment of participating in the study, practical reasons, or for regulatory or medical reasons (including slow enrolment). Should this be necessary, the patient must be seen as soon as possible and treated as a prematurely withdrawn patient. The investigator may be informed of additional procedures to be followed in order to ensure that adequate consideration is given to the protection of the patient's interests. The investigator will be responsible for informing the Institutional Review Board/Independent Ethics Committee (IRBs/IECs) of the early termination of the trial.

6 Visit schedule and assessments

Table 6-1 lists all of the assessments and indicates with an "x" when the visits are performed.

Patients should be seen for all study visits on the designated day, or as close to it as possible. Recommended study visit windows are +/- 2 days for visits 2 – 6, +/- 5 days for visits 7 – 12 and +/- 7 days for visits E1 – E3. The same visit windows are recommended for the lifestyle intervention visits associated to the study visits.

Missed or rescheduled visits should not lead to automatic discontinuation. Patients who prematurely discontinue the study for any reason should be scheduled for a visit as soon as possible, at which time all of the assessments listed for the final visit will be performed. In case of premature discontinuation during the core study the final visit is the week 28 visit, in the case of premature discontinuation during the extension period the final visit is the week 56 visit. At this final visit, all dispensed investigational product should be reconciled and the adverse event and concomitant medications reconciled on the CRF.

Table 6-1 lists assessments that are recorded in the clinical database (marked “X” if entered via the eCRF or “C” if entered centrally, e.g. via a central laboratory) and assessments that are source documentation only (marked “S”). Assessments that are source documentation only will not be entered into the eCRF.

If for any reason the subject is a screen failure, the subject may be re-screened. There is no restriction on the number of times a potential subject may be re-screened or on how much time must pass from the date of screen failure and the date of re-screening.

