OTH13	Patient included in the study and was on glucose lowering agent in treatment phase without stable dose for at least 12 weeks prior to baseline	INCLUDE IN EVERYTHING
OTH15	Subject has missed study extension visit	INCLUDE IN EVERYTHING
OTH17	No study visit performed due to Covid-19 but study drug administered at home	INCLUDE IN EVERYTHING
OTH18	Missed Visit due to COVID-19	INCLUDE IN EVERYTHING

OTH19	Visit not done at study site due to COVID-19	INCLUDE IN EVERYTHING
OTH20	Assessment/Procedure changed due to COVID-19	INCLUDE IN EVERYTHING
OTH22	Study Discontinuation due to COVID-19	INCLUDE IN EVERYTHING

The protocol deviation list is a live document and can be modified during the conduct of the trial. All the protocol deviations effecting patient safety and/or data reliability & efficacy will be considered major in nature and will be documented and included in Quality tolerance limits. The final list and exclusion codes will be confirmed before the CDBL.

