1.1 Study design

This study is a randomized, open-label, parallel-group, active comparator-controlled trial with two treatment arms. The design is shown in [Figure 1-1](#).

Figure 1-1 Study Design

R: Randomization

[figure not shown]
* During the extension period the lifestyle intervention can be continued by patients who have been in arm B during the core study, or it can be started by patients who have been in arm A. Participation in the lifestyle intervention during the extension period is **not** mandatory.

†Participation in the extension period itself is mandatory. Psoriasis treatment during the extension period can be chosen freely by the Investigator. No study drug is supplied during the extension period.

Extension period: After 28 weeks the study continues with an extension period, during which lifestyle intervention is offered to all patients, irrespective of their prior treatment arm. This means that patients of arm B, who are willing to, can continue their previously started lifestyle intervention program and patients of arm A, who are willing to, can start the lifestyle intervention program at the beginning of the extension period. **All patients, irrespective of their decision whether to start/ continue lifestyle intervention or not, have to participate in the extension period and visit their dermatologic study center for scheduled visits.** The extension period ends at week 56, where all patients complete the study. There will be no study

drug supply during the extension period. The treating physician can choose psoriasis therapy freely according to his/her discretion.

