2.6 Safety analyses

Safety analyses related to adverse event reporting will be based on the SAF. All the adverse from baseline till end of study (i.e. Week 56) will be reported cumulatively.

All Safety analyses for Extension period will be performed separately on the FAS.

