2.6.2 Deaths

Deaths occurring after entering the extension period will be listed and summarized separately, based on the FAS.

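### The extension SAP ties its safety-table population to core completion, so a patient who misses Visit 12 but attends the extension is left out of the extension death, laboratory, vital-sign, medication and PRO tables

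*SAP*

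**What the plan says.** Extension SAP 2.2 redefines the Full Analysis Set (FAS) for the extension report as "all patients who completed the Core phase of the study and either discontinued or entered the extension period". Its section 4 discloses the redefinition as a change from the protocol.

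The set is then used throughout that SAP. Section 2.6 states: "All Safety analyses for Extension period will be performed separately on the FAS". Section 2.6.2 states: "Deaths occurring after entering the extension period will be listed and summarized separately, based on the FAS". Sections 2.6.3 (laboratory), 2.6.4.2 (vital signs), 2.4.3 (concomitant medication) and 2.7 (PROs) name the same set. The exception is adverse event reporting: section 2.6 bases it on the Safety Set (SAF), cumulatively from baseline to Week 56.

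The meaning of completion comes from Protocol 5.6.1: "A patient will be considered to have completed the core study when the patient has completed the last visit planned of the core study". In Protocol Table 6-1 that visit is Visit 12, Week 28.

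On continued participation, Protocol section 6 states: "Missed or rescheduled visits should not lead to automatic discontinuation". Extension SAP 1.1 says that all patients "have to participate in the extension period and visit their dermatologic study center for scheduled visits".

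**The concern.** A safety table for a period should cover the patients observed in that period. The core SAP follows this principle, since its section 2.9 puts all safety analyses on the SAF. The extension SAP instead makes membership depend on one earlier visit.

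A patient without Visit 12 who attends E1, E2 and E3 has followed the protocol's instruction to stay on study, but is not a core completer and so is not in the extension FAS. Read literally, that patient's laboratory values, vital signs, medications and questionnaires are collected and then omitted from the extension tables. If that patient dies during the extension, the death is missing from the table in section 2.6.2 but present in SAF-based reporting, so two tables on deaths in one report could disagree.

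The situation is foreseeable. The deviation list in core SAP 5.4 contains an entry "Missed Visit due to COVID-19", although it does not say which visit.

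A second, weaker issue is the last clause of the definition. If it admits completers who stopped without entering, patients with no extension observation sit in the denominators of percentage tables.

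**Working it through.** The documents state no size for the extension FAS, so there is no figure to reproduce. The check is mainly textual.

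**Step 1. Is a Visit 12 misser who attends the extension in the set?**
- Membership requires core completion (extension SAP 2.2).
- Core completion requires the last planned core visit (Protocol 5.6.1), which is Visit 12 (Protocol Table 6-1).
- A missed visit does not end participation (Protocol section 6), and every patient is to attend the extension (extension SAP 1.1).
- Result: the patient is on study and outside the set. A Visit 12 that is only rescheduled still counts as completion and causes no exclusion.

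**Step 2. Are completers who never entered in the set?** The places in the extension SAP do not agree.
- Section 2.2 admits completers who either discontinued or entered. The natural reading includes those who stopped without entering. The other reading is those who entered, including those who later left.
- Section 2.3.1 gives demographics for patients who both completed the core and are entering. Section 2.3.2 gives them for the FAS.
- Section 3 expects every core completer to move to the extension.
- Result: ambiguous. If section 3 holds, there are no such patients.

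**Step 3. Extension Day 1.** Section 2.1.1.1 states: "The day when the patients complete core phase (Week 28) and enter extension period is defined as study Day 1 for Extension phase". The formula below it counts from the first extension assessment. For a patient without Visit 12 the sentence gives no Day 1, and only the formula does.

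**Step 4. Which tables are affected, and how?** Section 2.1.1 divides percentages by the whole relevant population or subgroup.

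| Extension table | Attender without Visit 12 | Completer who never entered (if admitted) |
|---|---|---|
| Deaths (2.6.2) | Death, if any, not counted; patient not in denominator | Denominator only, because only deaths after entry count |
| Notable laboratory values (2.6.3) | Lost from numerator and denominator | Denominator only |
| Continuous laboratory summaries (2.6.3) | Values lost | Raises displayed N; n, mean and SD unchanged |
| Vital-sign change (2.6.4.2) | Values lost | No effect on the statistics, since Week 36 and later values are required |
| Cumulative AEs, SAEs and fatal events (2.6, 2.6.1) | Retained through the SAF | Not applicable |

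**Step 5. Illustration of size (all inputs assumed).** Take C = 2 × 342 = 684 completers, borrowing the per-arm number from the sample size section; the documents do not say how many complete. Let m be attenders without Visit 12 as a share of C, from 0 to 5%, and u the share of completers who never enter, from 0 to 10%.

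Patients attending = C − uC + mC.
- u = 0, m = 1%: 684 + 7 = 691; omitted 7/691 = 1.0%.
- u = 0, m = 3%: 684 + 21 = 705; omitted 21/705 = 3.0%.
- u = 0, m = 5%: 684 + 34 = 718; omitted 34/718 = 4.7%.
- u = 10%, m = 0: 684 − 68 = 616; none omitted.

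Displayed percentage = true percentage × (1 − u). For a notable laboratory value with an assumed true rate of 4.0%:
- u = 0: 4.0%
- u = 3%: 3.88%
- u = 5%: 3.80%
- u = 10%: 3.60%

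**The case against.** A reader might infer that the set certainly keeps patients who never entered, and that the extension death, laboratory and vital-sign tables therefore all have wrong numerators and denominators. The documents do not support that. The clause is ambiguous, section 2.3.1 speaks of discontinuing during the extension, and section 3 expects every completer to enter. Vital-sign change and continuous laboratory statistics are not diluted by patients without extension values. The death numerator is short only if an omitted attender dies. The rule in section 2.1.1 for showing a row of missing values would also make unobserved patients visible in count tables.

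A reader might also infer that safety data are lost altogether. They are not. AE reporting to Week 56 stays on the SAF, and section 2.6.1 provides a listing of all AEs and separate summaries of deaths and SAEs. What can be short is the separate death table and the laboratory, vital-sign, medication and PRO tables.

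Selection by arm is possible but not shown. Change from Week 36 depends on attending Week 36 under any set, so no redefinition removes that selection.

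The remaining objections concern weight. The redefinition is disclosed, the extension SAP lists no statistical models (section 5.2), no count of affected patients is given, and the missed-visit deviation names no visit. The text of section 2.5 is not in the public document, so its missing-data rules could not be checked. These points limit the importance but do not answer step 1: a stated rule leaves observed patients out of a safety table. Disclosing the redefinition does not resolve that.

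**Conclusion.** The point holds in limited form. As written, the extension FAS excludes any patient who missed Visit 12 and attended the extension, and with that patient the observed laboratory, vital-sign, medication and PRO data and any entry in the extension death table. AEs, SAEs and fatal events should still be reported through the SAF.

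The possible admission of completers who never entered is secondary. It rests on one reading of an ambiguous clause that conflicts with section 2.3.1, it affects only percentage tables, and it is zero if all completers enter.

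The number of patients affected is not in the documents and may be small. The shares in step 5 are assumptions without a source in the protocol or SAP. They show only that the effect scales with the share concerned: even at u = 10%, a 4.0% rate would read as 3.6%. No primary or core-study result is affected.

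**What to change.** In extension SAP 2.2, add an Extension Safety Set for the extension safety tables: all SAF patients with documented extension entry or at least one extension-period assessment, regardless of whether Visit 12 was done. Do not admit patients on a reported event alone. That would make the denominator depend on the outcome, because an early withdrawer with a late event report would count while an identical withdrawer without one would not.

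In addition:
- align sections 2.2, 2.3.1 and 2.3.2 on one population;
- define extension Day 1 in section 2.1.1.1 for patients without Visit 12;
- use patients with at least one extension value as the denominator for notable laboratory percentages;
- if the completer set is kept, give it a name other than FAS, which has a different meaning in the protocol and the core SAP.

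The cost is a documented change of a descriptive population after database lock and a re-run of descriptive tables. The document history shows that an addendum was already issued after final lock, so a further documented correction is feasible. The number of patients concerned can be counted from the locked data and reported with it.

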2.3 Patient disposition, demographics, and other characteristics

2.3.1 Patient disposition

The number and percentage of patients entering the extension period, completed or discontinued the study during extension period, including reasons for discontinuation will be presented by treatment group for all patients.

Descriptive statistics for the background and demographic data will be provided for the patients completed the core study and entering the extension period. Continuous variables will be

summarized using N (the number of subjects in the analysis set), n (the number of subjects with available/imputed value), mean, median, SD, minimum and maximum.

Frequency counts and percentages will be presented for categorical variables for non-missing data. A row (category) denoted “Missing” will be included in count tabulations if a non-zero count of missing values is present. Percentages will be calculated using the number of patients in the relevant population or subgroup as the denominator. If a count of zero is obtained, the zero count and percentage will still be displayed. Two-sided 95% confidence intervals, if required, will be evaluated and reported for frequency percentages using the Clopper-Pearson Exact method.

2.3.2 Demographics and other characteristics

The following data will be summarized for FAS:

- age (in years, and year categories ≤ 65 , > 65)
- gender (male/female)
- childbearing status (able to bear children/post-menopausal/sterile - of childbearing age)
- race (Asian/Caucasian/Black or African American/Unknown/Other)
- smoking status (never/current/former)
- average pack year (former/current/overall)
- height (cm)*
- weight (kg, and weight categories < 90 , ≥ 90)
- body mass index (BMI) = weight (kg) / (height (meters))²
- waist circumference (cm)
- hip circumference (cm)
- waist to hip ratio = waist circumference (cm)/ hip circumference (cm)
- sitting pulse (bpm)
- systolic and diastolic blood pressure (mmHg)

*Height will be captured from the baseline vitals of the core study

2.4 Treatments (study treatment, rescue medication, concomitant therapies, compliance)

2.4.1 Study treatment / compliance

2.4.2 Study Compliance

2.4.2.1 Lifestyle intervention

Compliance as percentage of lifestyle intervention visits participated in will be calculated as the number of intervention visits attended (based on documented participation counts as given in the lifestyle intervention record eCRF page) divided by the number of lifestyle intervention visits scheduled per protocol until discontinuation. For dropouts/discontinuations, the

denominator will be adjusted to number of intervention visits participated scheduled per protocol until discontinuation.

Compliance is given by the formula:

Compliance (%) = $100 \times (\text{total no of lifestyle intervention visits participated}) / (\text{no. of lifestyle intervention visits scheduled})$

In the extension period, lifestyle intervention visits are scheduled at weeks 36, 44, and 56.

Compliance percentage will be summarized for the FAS (displaying totals) by categories (< 80% and ≥ 80% to 100%).

[figure not shown]
2.4.3 Concomitant and post therapies

[figure not shown]
Concomitant medications along with non-drug therapies will be summarized using the FAS.

Any medication given at least once between the day of entering the extension phase and the last day of the extension visit will be a concomitant medication, including those which were started before commencing extension period and continued into the extension period.

Medications will be presented in order of frequency, by Anatomical Therapeutic Classification (ATC) codes and grouped by anatomical main group. Preferred terms will be sorted by decreasing proportion and alphabetical order.

Tables will also show the overall number and percentage of subjects receiving at least one treatment in a particular ATC code.

2.6 Safety analyses

Safety analyses related to adverse event reporting will be based on the SAF. All the adverse from baseline till end of study (i.e. Week 56) will be reported cumulatively.

All Safety analyses for Extension period will be performed separately on the FAS.

2.6.1 Adverse events (AEs)

Treatment-emergent adverse events (events started after the administration of first dose of secukinumab in the Core phase or events present prior to the initiation of Core phase but increased in severity) will be summarized by preferred term. Additionally, AE(s) reported up to 84 days post Week 24 (i.e., till Week 36) will be considered as TEAEs.

All the AEs reported Week 36 onwards will be listed & summarized by preferred term up to last study assessment i.e., Week 56.

If a patient reports more than one AE with the same preferred term, the AE with the greatest severity will be presented. If a patient reports more than one AE within the same primary SOC, the patient will be counted only once with the greatest severity at the SOC level, where applicable. Furthermore, a listing of all AEs, including SAE, will be provided. SAEs will be summarized.

In the extension period, the treating physician is free to choose suitable psoriasis therapy for each patient. Summaries will be presented for AEs by severity and for chosen therapy (marketed secukinumab, Novartis or Non-Novartis products) related AEs.

Separate summaries will be provided for death, SAE, other significant AEs leading to discontinuation of study grouped by therapy chosen by treating physician.

2.6.2 Deaths

Deaths occurring after entering the extension period will be listed and summarized separately, based on the FAS.

2.6.3 Laboratory data

The summary of laboratory evaluations will be presented for three groups of laboratory tests (hematology, clinical chemistry, and urinalysis) separately, for extension period, based on the FAS. Data for hematology, clinical chemistry, and urinalysis will be listed separately. All the laboratory parameters and markers with values below Limit of quantification (LOQ) will be reported as LOQ/2. Descriptive summary statistics for each study visit will be presented.

These descriptive summaries will be presented by laboratory test group, laboratory test. An additional summary table will be reported for the patients chosen for being administered secukinumab by the physician.

The below-mentioned laboratory parameters will be descriptively summarized. Frequencies and percentages will be presented for patients with clinically notable laboratory values, for the below-mentioned selected lab parameters:

Clinically notable laboratory values

Liver Function and Related Variables

- ALT (SGPT): $> 3 \times$ Upper Limit of Normal (ULN)
- AST (SGOT): $> 3 \times$ ULN
- Total bilirubin: $> 1.5 \times$ ULN
- Alkaline phosphatase: $> 2 \times$ ULN

Renal Function and Electrolyte Variables

- Creatinine (serum): $> 1.5 \times$ ULN

Hematology Variables

- Hemoglobin: ≥ 20 g/dL decrease from week 36
- Platelet count: $<$ Lower Limit of Normal (LLN)
- White blood cell count: $< 0.8 \times$ LLN
- Neutrophils: $< 0.9 \times$ LLN
- Eosinophils: $> 1.1 \times$ ULN
- Lymphocytes: $> 1.1 \times$ ULN

Clinically significant abnormal laboratory values will also be summarized based on the FAS.

